7.6.3 Other Endpoint Analysis

An initial assessment will be completed during the primary efficacy analysis as follow-up data allows with a complete analysis to be provided with the full study results for applicable other analyses. Additionally, the other analyses will be conducted on other efficacy populations as needed.

7.6.3.1 Comparison of baseline characteristics in subjects successful with one dose of RBX2660 vs. those who were unsuccessful.

A multivariate analysis or regression analysis will be used to identify predictors (if any) for subject success with one RBX2660 dose vs. those who were unsuccessful.

7.6.3.2 Cdiff32 scores at Screening, 1-week, 4-week, and 8-week assessment visits, and 3 and 6 month phone assessments.

Changes from Screening in the Cdiff32 scores will be summarized using descriptive statistics by treatment arm. Last observation carried forward (LOCF) will be used to impute missing post-baseline data. No inferential statistics will be performed.

7.6.3.3 Subject fecal microbial composition at Screening, and 4 and 8- weeks and 3 and 6 months after blinded study treatment.

Descriptive statistics will be used to present the changes from Screening fecal microbial composition to those at 4 weeks, 8 weeks, 3 months and 6 months after blinded study treatment for those subjects treated with RBX2660 and those receiving Placebo.

7.6.3.4 Charlson Comorbidity Index at Screening, 8 week visit, and 3-, 6- month phone assessments.

A comorbidity index score will be documented for all subjects at Screening and compared to subsequent scores at 8 weeks, 3 months and 6 months. An initial assessment will be completed during the primary efficacy analysis as follow-up data allows with a complete analysis to be provided with the full study results. Additional analysis may be done of Placebo subjects who

were documented treatment failures after blinded treatment then treatment successes following unblinded RBX2660 treatment.

7.6.3.5 Atlas score for CDI severity of qualifying CDI.

Quantification of CDI severity scores for subjects at the time of the CDI recurrence that qualified them for enrollment into the study based on the ATLAS Scoring System. Data from the qualifying CDI event will be used (see table below), including the protocol required eligibility criteria of treatment with systemic antibiotics prior to randomization. However, if data points are not available, baseline data may be substituted.

Parameter	0 Points	1 Point	2 Points
Age (years)	< 60	60 – 79	≥ 80
Temperature (°C)	≤ 37.5	37.6 – 38.5	≥ 38.6
Leukocyte count (total)/mm ³	< 16,000	16,000 – 25,000	> 25,000
Albumin (g/L)	> 35	26 – 35	≤ 25
Systemic concomitant antibiotics during CDI RX	No	-	Yes

7.6.3.6 Recurrence of CDI within 8 weeks in Placebo subjects who were documented study treatment failures and then received RBX2660 through open-label.

Treatment success for documented Placebo failures after receiving RBX2660 will be completed using a Chi-square test comparing the treatment success of blinded placebo subjects as compared to the success of placebo subjects who received RBX2660. This analysis will be completed with the full study results rather than the primary efficacy analysis as it requires data on the outcome following any unblinded RBX2660 enemas received.

7.6.3.7 Recurrence of CDI within 8 weeks of unblinded (open-label) RBX2660 treatment in subjects who received a blinded dose of RBX2660.

Determine the treatment success rate of those subjects randomized to RBX2660 who were deemed an initial treatment failure then went on to receive an unblinded RBX2660 enema (two RBX2660 enemas). This success rate will be calculated at 8 weeks following the second

RBX2660 enema and compared to the blinded success rate of the RBX2660 arm using a Chi-square test.

7.6.3.8 Occurrence of CDI through 6 months in all subjects receiving a single dose of RBX2660.

Determine the combined treatment efficacy for RBX2660 randomized subjects plus Placebo randomized subjects who were documented failures after blinded treatment then received a unblinded RBX2660 enema. This analysis will be completed with the full study results rather than the primary efficacy analysis as it requires data on the outcome following any unblinded RBX2660 enemas received. Both treatment success and treatment durability will be analyzed;

- Treatment success rate for the prevention of CDI recurrence
- Treatment success rate for the prevention of new CDI episodes (those with onset occurring beyond 8 weeks after study treatment)

7.6.3.9 Concentration of vancomycin resistant enterococcus in stool samples for subjects who were carriers at baseline.

Lab generated values for the presence of vancomycin resistant enterococcus based on submitted stool samples at baseline and at 1-, 4-, 8-weeks, and 3 and 6 months will be assessed for all subjects to identify any trends in the clearance of vancomycin resistant enterococcus following enema treatment.

*7.6.3.10 Presence of *C. difficile* in stool samples at Screening, and 4-weeks, 8-weeks, 3-months and 6-months after study treatment.*

Lab generated values for the presence of *C. difficile* based on submitted stool samples at baseline and at 1-, 4-, 8-weeks, and 3 and 6 months will be assessed for all subjects to identify any trends in the clearance of *C. difficile* following enema treatment.

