3.3 Other Objectives

1. To confirm the safety and tolerability of RBX2660.
2. To identify baseline characteristics predictive of efficacy outcomes.
3. To characterize the changes from baseline fecal microbial composition in subjects treated with RBX2660 as compared to Placebo.
4. To characterize the changes from baseline comorbidities in subjects treated with RBX2660 as compared to Placebo.
5. To evaluate health-related quality of life for CDI as measured by the Cdiff32 questionnaire.
6. To characterize the baseline severity of CDI in subjects with documented CDI recurrence.

7. Evaluate treatment success of RBX2660 in Placebo subjects who are documented study treatment failures then went on to receive RBX2660.
8. Assess the ability of more than one dose of RBX2660 to prevent CDI recurrence.
9. Assess the combined treatment success of all subjects receiving a single dose of RBX2660 during the study both to prevent recurrent CDI as well as prevent new CDI episodes.
10. Assess the clearance rate of vancomycin resistant enterococcus in subjects who are carriers at baseline.
11. Assess the clearance of *C. difficile* following enema treatment at 4 and 8-weeks and 3 and 6 months after blinded study treatment in subjects receiving RBX2660 and those receiving Placebo.

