An analysis of time to CDI recurrence after completion of the assigned blinded treatment will be analyzed and presented by the Kaplan-Meier procedure and median duration presented by days (and weeks) using the ITT, mITT, and PP populations. The Kaplan-Meier estimate of the median time (days) and the associated 95% confidence interval will be presented for each treatment group. A graphic presentation of the Kaplan-Meier estimates will supplement the tabular presentation. Between group comparisons will be performed using the stratified log-rank test based on the stratification factor at randomization. The corresponding hazard ratio of the treatment effect along with the 95% confidence interval will be calculated using a Cox proportional hazard model with treatment and the stratification factor at randomization as explanatory variables.

Time to CDI recurrence is defined as the number of days from enema administration to first assessment indicating recurrence for those subjects who were deemed Treatment Failures with CDI recurrence. All subjects who are Indeterminate or discontinued for any reason prior to assessment of efficacy will be censored at the last assessment date at/prior to Week 8. For the analysis of Time to CDI recurrence within 8 weeks, all subjects considered as a treatment success will be censored at the date of their 8-week assessment. For the analysis of Time to CDI

recurrence through 6 months, all subjects considered to have achieved sustained clinical response will be censored at the date of their 6-month assessment.

Finally, the sensitivity of the primary efficacy endpoint will be assessed in a multivariate logistic regression adjusting for possible interactions of the following covariates with treatment group: age (< 65 years, \geq 65 years), sex (Female, Male), race group (White, Non-white), ethnicity (Hispanic-Latino, not Hispanic-Latino), site geography (outside the US, Eastern US*, Southern US*, Northern US*, Western US*), randomization strata (i.e., treatment received at the qualifying event) and number of previous episodes of CDI recurrence at baseline. Other baseline variables will be compared for balance using the appropriate statistical test. This analysis will be performed on all analysis populations where at least 20 subjects in each sub-group are available for analysis to fully understand the observed treatment effect.

*States included in the identified US geographical regions are as follows:

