8.8 Examination of Subgroups

Subgroup analysis of age (< 65 years, ≥ 65 years), sex (Female, Male), race group (White, Non-white), ethnicity (Hispanic-Latino, not Hispanic-Latino), site geography (outside the US, Eastern

US*, Southern US*, Northern US*, Western US*) and number of previous episodes of CDI recurrence at baseline will be conducted on the primary efficacy analysis if a sufficient sample size exists for each subgroup. The primary efficacy analysis will also be conducted based on vancomycin use for the qualifying CDI episode \leq 14 days and $>$ 14 days using subjects who were stratified based on Vancomycin Alone. These analyses will include all analysis populations (mITT and PP) to understand any differences.

*States included in the identified US geographical regions are as follows:

- Eastern US: Connecticut, Delaware, District of Columbia, Maine, Maryland, Massachusetts, New Hampshire, New Jersey, New York, Ohio, Pennsylvania, Rhode Island, Vermont, Virginia, West Virginia
- Southern US: Alabama, Arkansas, Georgia, Florida, Kansas, Kentucky, Louisiana, Mississippi, North Carolina, Oklahoma, South Carolina, Tennessee, Texas
- Northern US: Illinois, Indiana, Iowa, Michigan, Minnesota, Missouri, Nebraska, North Dakota, South Dakota, Wisconsin
- Western US: Arizona, California, Colorado, Idaho, Montana, Nevada, New Mexico, Oregon, Utah, Washington, Wyoming

Other sub-groups may be considered if there are enough subjects in each group such as; qualifying CDI event treated as inpatient vs. outpatient, the severity of the qualifying event based on the ATLAS scores, treatment length or type of antibiotics taken at the time of the CDI qualifying event, and others yet undetermined.

Cochran-Mantel-Haenszel tests will be used to assess homogeneity of the odds ratios in the subgroups.

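### SAP 7.6.3.1 seeks predictors of success after RBX2660 without a placebo comparator, so it cannot separate prognosis from treatment benefit; Charlson index and ATLAS score have no firm interaction analysis elsewhere

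*SAP*

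**What the plan says.** Item 2 of SAP 3.3 (also Protocol 2.3) is "To identify baseline characteristics predictive of efficacy outcomes". SAP 7.6.3.1 is headed "Comparison of baseline characteristics in subjects successful with one dose of RBX2660 vs. those who were unsuccessful". Its text is one sentence, under which a multivariate or regression analysis "will be used to identify predictors (if any) for subject success with one RBX2660 dose vs. those who were unsuccessful". It gives no covariate list, no analysis population, no interaction term and no placebo comparator.

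Two other sections bear on the question.

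- SAP 7.6.1.2 plans a "multivariate logistic regression adjusting for possible interactions of the following covariates with treatment group". The list is age, sex, race, ethnicity, site geography, randomization stratum and number of previous CDI episodes. It is run on populations "where at least 20 subjects in each sub-group are available for analysis to fully understand the observed treatment effect".
- SAP 8.8 repeats the primary analysis in subgroups of the same factors apart from the stratum, adds duration of vancomycin use, and states that "Cochran-Mantel-Haenszel tests will be used to assess homogeneity of the odds ratios in the subgroups". ATLAS severity comes only in a further list, introduced by "Other sub-groups may be considered if there are enough subjects in each group such as".

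Charlson index is in neither section. SAP 7.3 nevertheless has both Charlson and ATLAS scored for every subject at baseline.

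**The concern.** A comparison of successes with failures inside one treatment group tests whether a characteristic is related to recurrence in subjects given RBX2660. Two quite different characteristics can produce such a relation: one that lowers the risk of recurrence whatever is given, and one that changes how much RBX2660 adds. The regression sees only their sum.

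The plan's own rates make this more than a formality. If 47% would succeed on placebo and 69% on RBX2660, then about 47/69 = 68% of the RBX2660 successes would be expected without the product, provided that RBX2660 never causes a recurrence. A list of predictors of RBX2660 success could then be read as a guide to who benefits, when it may largely describe who was at low risk. The randomized placebo arm can tell the two apart, and its data are collected anyway.

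**Working it through.** **Inputs from the documents.** Success 69% on RBX2660 and 47% on placebo, 2:1 allocation, 240 evaluable subjects (160/80), up to 270 treated (180/90): SAP 4.4. Two-sided 0.05 as the default level: SAP 8.1.

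**Inputs assumed.** A two-level characteristic with 50% prevalence, and the odds ratios (OR) shown below. The documents give neither.

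**Step 1, the plan's own figure.** SAP 7.6.3.1 states no figure, so the check is on the sample size that supplies the rates. With pooled rate (0.47 + 2 × 0.69)/3 = 0.617, the placebo-arm size is

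n = [1.96 √(1.5 × 0.617 × 0.383) + 1.282 √(0.47 × 0.53 + 0.69 × 0.31/2)]² / 0.22² = 77.1, so 78.

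That gives 78 + 156 = 234 subjects, close to the stated 240. Power at 80/160 is 91.0%, in line with the stated value above 90%.

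**Step 2, the two tests.** Let L1 and L0 be the log odds of success at the two levels of the characteristic.

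- RBX2660-only: z = (L1 − L0 in RBX2660) / √(sum of the two RBX2660 variances).
- Interaction: z = [(L1 − L0 in RBX2660) − (L1 − L0 in placebo)] / √(sum of all four variances).

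Each variance is 1/[n p (1 − p)]. Success over both levels was held at 69% and 47%.

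**Step 3, one case by hand** (160/80, OR 2). RBX2660 success is 61.7% and 76.3%, with 80 subjects per level.

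- RBX2660-only: variance 1/(80 × 0.617 × 0.383) + 1/(80 × 0.763 × 0.237) = 0.053 + 0.069 = 0.122. Then z = 0.693/0.349 = 1.98, and the chance of exceeding 1.96 is about 51%.
- Interaction, when placebo is flat at 47% (40 per level): add 2/(40 × 0.47 × 0.53) = 0.201, total 0.323. Then z = 0.693/0.568 = 1.22, and the chance is about 23%.

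**Step 4, simulation** (200,000 trials per row, 160/80).

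| Characteristic | RBX2660-only test significant | Interaction test significant |
|---|---|---|
| Purely prognostic, OR 1.5 | 21% | 5% |
| Purely prognostic, OR 2 | 51% | 5% |
| Purely prognostic, OR 3 | 88% | 5% |
| RBX2660 flat at 69%; placebo 38.5% vs 55.5% | 5% | 23% |
| RBX2660 flat at 69%; placebo 33.7% vs 60.3% | 5% | 47% |
| Placebo flat at 47%; OR 2 under RBX2660 | 51% | 23% |
| Placebo flat at 47%; OR 3 under RBX2660 | 88% | 48% |

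At 180/90 the prognostic rows become 23%, 56% and 91%, with the interaction test still at about 5%.

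Rows 2 and 6 are the telling pair. The RBX2660-only test gives 51% in both, although the first characteristic leaves the treatment odds ratio unchanged and the second acts only under RBX2660.

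**Step 5, what the interaction test can deliver.** At 180/90, with placebo flat, its power is 53%, 72% and 83% at interaction odds ratios of 3, 4 and 5.

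**The case against.** The case against is substantial, and most of it stands.

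- The objective speaks of efficacy outcomes and not of benefit relative to placebo. SAP 7.6.3.1 promises predictors of success after one RBX2660 dose, which is what its regression estimates. A reader might infer that the analysis answers the wrong question; the documents do not support that.
- A reader might take the 21% to 88% as false-positive rates. They are not. In those rows the characteristic truly is associated with success under RBX2660, and the test is right to find it.
- A reader might conclude that the RBX2660-only test shows only who is at low risk and is weak for real differences in benefit. The last two rows of the table refute this as a general statement: when a factor acts only under RBX2660, that test finds it more often than the interaction test does. It cannot say which kind of factor it has found.
- A reader might conclude that the plan leaves the placebo arm out when asking in whom RBX2660 works. SAP 7.6.1.2 and 8.8 show otherwise for their listed factors.
- More interaction tests at this sample size will rarely be conclusive.

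What the objection does not remove is the gap outside those lists. Charlson index has no planned interaction analysis, and ATLAS has only a discretionary subgroup. Nor does SAP 7.6.3.1 refer to either section or tell the reader how to interpret its predictors. Its population is also open: SAP 7.6.3.8, on single-dose subjects, counts placebo failures later given open-label RBX2660. Read that way, 7.6.3.1 would include subjects selected because they had already recurred.

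**Conclusion.** The concern holds in a limited form. SAP 7.6.3.1, taken alone, estimates who does well after RBX2660 and cannot divide that into prognosis and benefit. Under the assumed 50% prevalence and a constant treatment odds ratio, a purely prognostic factor with an odds ratio of 1.5 to 3 would appear on its list in 21% to 88% of trials of 160/80. A modifier that leaves RBX2660 success flat would appear in only about 5%. Other prevalences or odds ratios would change these figures but not the reasoning.

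The plan already covers effect modification for the main demographic and CDI-history factors, so the practical gap is Charlson index, ATLAS score, and the labelling of the results. This is a minor, exploratory-level improvement. The primary and secondary endpoints, alpha and sample size are untouched.

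**What to change.** In SAP 7.6.3.1:

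1. Fit the model to both randomized arms on the blinded 8-week outcome, with treatment, characteristic and treatment-by-characteristic terms. This also settles the population.
2. Include at least Charlson index and ATLAS score, and cross-refer to 7.6.1.2 for the factors already listed there.
3. Report the association within each arm, labelled prognostic, and the interaction estimates with 95% confidence intervals, all labelled exploratory.
4. Keep the RBX2660-only regression, labelled as association with success under RBX2660 and not as evidence of who benefits.

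The cost is a few sentences and a few model runs on data already collected. The drawback is imprecision: interaction power passes 80% only at an interaction odds ratio of about 5, so the intervals will be wide and few factors can be called predictors of benefit.

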3.8. Management of Treatment Failure

Following blinded treatment, subjects meeting the protocol definition of treatment failure may be scheduled for administration of an unblinded RBX2660 enema within 21 calendar days of failure determination. In order to receive the unblinded RBX2660 enema, the site must provide documentation of meeting all treatment failure criteria as defined by the protocol. If the subject has a subsequent treatment failure after the unblinded RBX2660 enema, the subject can be given another therapy as deemed appropriate by the treating investigator.

Without conclusive failure documentation, an unblinded RBX2660 will not be provided for administration.

Treatment failures are required to be entered in the study database shortly after determination of failure to allow for sponsor awareness and assurance that an unblinded RBX2660 can be provided if requested.

If antibiotics are given to control symptoms, a 24-72hr washout period prior to administration of an unblinded RBX2660 enema is required. If the subject will have the unblinded enema, it needs to be administered within 21 calendar days of failure

determination. The use of antibiotics prior to an unblinded RBX2660 enema is at the discretion of the investigator.

If a subject receives an unblinded RBX2660 enema, the follow-up requirements will restart from the day of the unblinded RBX2660 enema according to the same schedule as required for the blinded portion of the study. This results in completion of a new subject diary for up to 7 days after treatment; in-office visits at 1-, 4- and 8-weeks as well as telephone calls at 2-, 3- and 6- weeks and at 3 and 6 months after the last RBX2660 treatment.

Treatment failures who do not receive an unblinded RBX2660 enema will continue to follow their original schedule of assessments for the duration of the study based on the blinded study enema.

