solicited events from the date of enrollment to the 1-week follow-up visit after receiving the blinded study enema. The diary will be collected and reviewed at the baseline visit prior to blinded enema administration, and then collected and reviewed at the 1-week follow-up visit following enema administration.

Subjects who are deemed failures following the blinded treatment per the pre-specified treatment failure definition may elect to receive an unblinded RBX2660 enema. The unblinded enema is to be administered within 21 calendar days of failure determination. If a subject has a CDI episode on-study and the treatment plan is to pursue a treatment other than that specified in the protocol, the subject will be exited prior to receipt of the non-study treatment (ex. fecal microbiota transplant).

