4.4 Determination of Sample Size

To demonstrate a 69% success with one dose of the RBX2660 treatment group vs. 47% success in the Placebo control group, 240 subjects are required (power > 90%, nominal 2.5% type I error rate). Up to an additional 30 subjects will be enrolled to allow for a 10% loss-to-follow up rate, for a total of approximately 270 subjects. Considering the 2:1 randomization, this results in approximately 180 subjects in the RBX2660 arm and 90 subjects in the Placebo arm. Enrolled subjects who have signed consent and withdraw for any reason prior to administration of the first blinded enema will be replaced without counting toward the sample size cap. Replacement subjects will be randomized to ensure proper blinding.

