8.3 Handling of Dropouts or Missing Data

No imputations will be used in analyses/summaries. However, a last observation carried forward analysis will be used for evaluation of the Cdif 32 scores. Missing safety data will not be imputed beyond the adjustments for adverse event data mentioned in Section 6.5.2.

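### LOCF for Cdiff32 fills scores that are missing because of recurrence, in a larger proportion of placebo than RBX2660 subjects, and the SAP does not say whether scores after open-label RBX2660 are used

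*SAP*

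**What the plan says.** - **Imputation.** SAP 7.6.3.2 summarises change from Screening in Cdiff32 by treatment arm at weeks 1, 4 and 8 and months 3 and 6. The missing-data rule is "Last observation carried forward (LOCF) will be used to impute missing post-baseline data", and "No inferential statistics will be performed". SAP 8.3 confirms it: "a last observation carried forward analysis will be used for evaluation of the Cdif 32 scores".
- **Collection.** Protocol Table 6-1 and Sections 6.8 to 6.13 collect Cdiff32 at those visits and at the unscheduled possible-recurrence visit.
- **Exit.** Under SAP 4.1, when the plan for an on-study CDI episode is a treatment outside the protocol, "the subject will be exited prior to receipt of the non-study treatment".
- **Open-label RBX2660.** Under Protocol 3.8, "the follow-up requirements will restart from the day of the unblinded RBX2660 enema". Failures who do not take it stay on their original schedule.
- **Windows.** SAP 6.2.1 counts days from the first enema. SAP 6.2.2 sets month 3 at days 76 to 104 and month 6 at days 166 to 194.
- **Open-label data elsewhere.** SAP 7.7 splits adverse events after week 8 into four groups by randomised arm and receipt of open-label RBX2660. The SAP has no such split for Cdiff32, and no rule on whether scores after open-label treatment are used, set to missing or shown apart.

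**The concern.** LOCF gives a fair picture only if a subject's last score stands in well for the one not observed. Here the usual reasons for a missing late score are leaving the study over a CDI episode or moving to open-label RBX2660. Both follow from recurrence, and recurrence is expected in a larger share of placebo subjects. The month-3 and month-6 arm means would therefore mix observed scores with carried scores in different proportions by arm.

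This is the only analysis specified for the quality-of-life objective (objective 5 in Protocol 2.3 and SAP 3.3). No test is planned, but a table laid out by arm will be read as a comparison of arms.

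**Working it through.** **1. The planning rates.** SAP 4.4 reads: "To demonstrate a 69% success with one dose of the RBX2660 treatment group vs. 47% success in the Placebo control group". Its stated total for this aim is 240, with power above 90% at a nominal type I error of 2.5%. With 2:1 allocation, read as two-sided 5%, pooled variance and no continuity correction:

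- mean rate = (0.47 + 2 × 0.69)/3 = 0.6167
- placebo n = [1.960 × √(0.6167 × 0.3833 × 1.5) + 1.2816 × √(0.47 × 0.53 + 0.69 × 0.31/2)]² / 0.22² = (1.167 + 0.765)²/0.0484 = 77.1, so 78
- total = 3 × 78 = 234; power at 80 placebo and 160 RBX2660 subjects is 91.0%

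This agrees with 240, so the planning rates can be used below.

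**2. Who can be exposed.** Failure by week 8 is 1 − 0.47 = 53% on placebo and 1 − 0.69 = 31% on RBX2660.

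| | Placebo | RBX2660 |
|---|---|---|
| Share failing by week 8 | 53% | 31% |
| Expected number | 0.53 × 90 = 47.7 | 0.31 × 180 = 55.8 |

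The share is 0.53/0.31 = 1.71 times as high on placebo, but the count is lower there. Phase 2B gives the same ordering of shares: 54.5% vs 33.3% from Protocol 1.5.2 (ratio 1.64) and 56.8% vs 40.5% from Table 1 of the SAP appendix (ratio 1.40).

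These are upper bounds for the route through 8-week failure, because failures who stay on the original schedule are still assessed. In Phase 2B, Protocol 1.5.2 implies 44 − 20 = 24 placebo failures and has 24 in the open-label denominator, which suggests uptake can be near complete. At 50% exposure the shares are 26.5% and 15.5%.

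**3. Exits.** After exit for non-study therapy there is no later score. LOCF repeats the last one, from at or before the recurrence, to month 6. The SAP does not say whether the unscheduled-visit score can be the one carried.

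**4. Open-label recipients.** Let U be the day of the open-label enema, counted from the first enema as day 1. On-time Cdiff32 assessments then fall on U+7, U+28, U+56, U+89 and U+179.

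- U+179 ≤ 194 requires U ≤ 15.
- U+89 ≥ 166 requires U ≥ 77.
- The month-6 window is therefore empty for U from 16 to 76.
- If phone visits use their full ±14 days, the limits become U ≤ 29 and U ≥ 63. The window is still empty for U from 30 to 62.

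Failure by day 57 plus the 21 days allowed puts the latest U at about 78. The SAP schedule header gives 10 days where the protocol and SAP 4.1 give 21. These must be reconciled, but with 10 days U would end at about 67, still inside the empty range.

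The documents give no distribution for U. As a rough check, take the exponential times of SAP 6.4.2 and on-time visits. U ≤ 15 requires recurrence within 14 days, and U ≥ 77 requires failure on day 56 or later.

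- Placebo: (1 − 0.47^(14/56))/0.53 = 32% at most early; (0.47^(55/56) − 0.47)/0.53 = 1% at most late; at least 66% in the empty range.
- RBX2660: (1 − 0.69^(14/56))/0.31 = 29%; (0.69^(55/56) − 0.69)/0.31 = 1%; at least 70% in the empty range.

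Month 3 differs: a post-open-label score falls in its window at 10 of 11 values of U tried between day 10 and day 78.

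**5. What LOCF puts into an empty month 6.**

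- Blinded-phase scores only: a score from at or before the recurrence is frozen. A poor recurrence score makes that arm look worse than it is. A good score from before the recurrence hides a real deficit.
- All scores: a score after open-label RBX2660 is carried. In the placebo arm this counts any RBX2660 benefit as placebo and shrinks the difference.

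**6. Conditional size.** Let u be the share of failures with a carried blinded-phase score, and D the shortfall of that score against the true month-6 score, equal in both arms. The shift in the arm difference is (0.53 − 0.31) × u × D = 0.22 × u × D. The documents give no D. Assumed values show the range:

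| D (points) | u = 1 | u = 0.5 |
|---|---|---|
| −10 | −2.2 | −1.1 |
| 0 | 0 | 0 |
| 10 | 2.2 | 1.1 |
| 20 | 4.4 | 2.2 |
| 30 | 6.6 | 3.3 |

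**The case against.** The strongest reply is that recurrence does not end Cdiff32 collection. Failures who decline open-label RBX2660 keep their visits, those who accept it get a full new schedule, and CDI antibiotics newly prescribed for a recurrence are allowed on study. Only exits leave truly missing scores, and no SAP rule discards post-open-label scores. This stands as far as it goes. It makes 53% and 31% ceilings, and it means month 3 usually contains a score. It does not rescue month 6, where the restarted schedule misses the first-enema window for most values of U and LOCF applies even if post-open-label scores are meant to be used.

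A reader might also draw stronger conclusions that the documents do not support:

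- **That SAP 8.3 contradicts 7.6.3.2.** It opens with "No imputations will be used in analyses/summaries", but its next sentence makes Cdiff32 the exception. The two sections agree.
- **That many more placebo subjects are affected.** This is true of the proportion, which drives an arm mean, but not of the count (about 48 against 56).
- **That LOCF manufactures a difference of 0.22 × D in favour of RBX2660.** That requires every failure to lose all later blinded-phase scores, every carried value to be a recurrence score, post-open-label scores to be discarded, and every subject to have recovered by month 6. None of this is in the SAP, and part of any difference would reflect real recurrence.

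Finally, Cdiff32 is an exploratory, descriptive endpoint. That is correct and limits the importance of the point.

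**Conclusion.** The point holds as a weakness in a descriptive analysis. LOCF is prespecified where missingness depends on outcome and is proportionally more common on placebo, by at most 53% to 31% at the planning rates for the 8-week-failure route. For exits, it freezes a score from at or before recurrence. For most open-label recipients, it fills month 6 with a blinded-phase or a post-RBX2660 score under a rule the SAP does not state. Neither choice gives a month-6 arm mean that can be read plainly.

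The distortion can go either way and its size is not established. The tabulated shifts rest on assumed values of D and u. The window result rests on counting from the first enema, as SAP 6.2.1 does, and on visits near their due dates. Calling most open-label recipients affected also rests on the exponential times of SAP 6.4.2 and on uptake not depending on when the recurrence occurs. No hypothesis test, error rate, success criterion or efficacy claim is touched. The change is worth making because it is cheap, but nothing confirmatory depends on it.

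**What to change.** 1. Delete LOCF for Cdiff32 from SAP 7.6.3.2 and 8.3.
2. Summarise observed change from Screening by visit and arm, with the number of subjects contributing to each mean.
3. State how scores after open-label RBX2660, after exit and from the unscheduled recurrence visit are used. Present post-open-label scores separately, timed from the open-label enema and split by randomised arm, following the grouping in SAP 7.7.
4. Optionally add a supportive mixed model for repeated measures on blinded-phase scores (treatment, visit, treatment by visit, Screening score). State that it assumes data missing at random and does not describe how subjects fared after open-label treatment.

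No new data are needed. The cost is SAP wording, one extra table and, if chosen, one standard model. Numbers at months 3 and 6 will be smaller, and subjects still observed in the blinded phase will be a selected group. Showing the contributing counts makes that visible.
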